Greenwashing Manipulations (Sessions 1-9): During behavioral sessions participants will have the opportunity to smoke at least 1 of 2 types of cigarettes (topography sessions will involve the opportunity to smoke 1 type per session, whereas both types will be available during behavioral economic sessions and participants can choose to smoke either or both). Participants will be exposed to advertising for two different novel cigarette brands. One brand will be advertised using greenwashing tactics, while the other brand will have control advertising lacking the greenwashing tactics. To avoid a brand x greenwashing confound, the brand that is advertised with greenwashing materials will randomly vary across participants (e.g., Participant 1 may see Brand A advertised with greenwashing; Participant 2 may see Brand A advertised with the control ads). Participants will be exposed to the materials in two ways designed to replicate real world exposure to cigarette marketing for 30 minutes before sessions. First, posters will be placed on the walls to mimic advertising in retail settings. Participants will also be given printed information about each brand, designed to mimic direct mail advertisements, and may view this information as long as they like during the 30 minutes. These advertising materials and cigarette packs will remain in the room during topography and behavioral economic sessions. Unknown to the participants, both brands of cigarettes (Brand A and Brand B) will be the same commercial brand of cigarette. The study team will purchase cigarettes from a local store that sells commercially-available cigarettes. The study team will repackage these cigarettes into new packages that have either greenwashing elements or a control package that is similar, but without greenwashing elements. Although the two brand names and advertisements will be the same across participants, the actual commercial brand of cigarette used will be individualized for each participant to roughly the nicotine and menthol content for the participants typical brand of cigarettes. We will also ensure that it is a brand that lacks distinctive markings on the cigarettes that would allow for identification. Because this is within-subjects research that tests the effects of greenwashing, the brand used is arbitrary aside from the above considerations.

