cigarettes in our laboratory (IRB00107178). In 4 sessions, a demand curve will be generated for greenwashed cigarettes while control cigarettes will be available at a fixed price throughout. Specifically, in one session, both types of cigarettes will be concurrently available for the same fixed, low behavioral price (10 plunger pulls for a bout of 3 cigarette puffs). In the other 3 sessions, the control cigarettes will be available for 10 pulls, while the greenwashed cigarettes will be concurrently available for 100, 1000, or 10000 pulls (varying across the 3 sessions). This models the realistic situations in which greenwashed cigarettes are available at higher prices than other cigarettes. Then in another 3 sessions which provide an important comparison condition, we will assess the opposite situation, in which price for control cigarettes is 100, 1000, or 10000 pulls across sessions (the session in which both are available for 10 pulls will have already been conducted), and greenwashed cigarettes are available at a fixed price of 10 pulls throughout. The order of the 7 behavioral sessions (with different price combinations) will be randomized for each participant.

During sessions, after confirming the CO breath requirement, the participant will take 1 puff of each type of cigarette. A 3 hour self-administration session will start 30 minutes after the initial puffs. Initial puffs will standardize the time since last smoking across all participants and sessions. Participants will complete each session in 1 of 4 existing identical ventilated smoking rooms, each equipped with a computer connected to a response console used to collect data. The console will have two Lindsley-type response plungers (custom modeled after Gerbrands No. G6310, Ralph Gerbrands Co., Arlington, MA, USA) horizontally spaced equidistantly along the front of the console. A force of 20 N will be required to operate the plunger and register a response. Depending on the response requirement of the session, a certain number of plunger pulls will result in controlled self-administration of cigarette puffs (described in more detail in puffing procedure subsection below). Either the left or right side plunger will be randomly associated across participants with either the greenwashed or control cigarettes. We will supply all cigarettes.

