Demand Metrics: Reinforcement will be assessed by the 2 essential demand metrics: demand intensity and demand elasticity; which are calculated with nonlinear regression using the exponential demand equation (Hursh & Silberberg, 2008). Auxiliary metrics (Pmax, Omax, breakpoint) will also be examined, although these are derivative of the essential metrics. Demand elasticity and demand intensity will be calculated for each cigarette type (greenwashed or control) as it escalates in price and the alternative cigarette price remains fixed. Cross-price elasticity will be calculated to quantify the effect of increasing greenwashed cigarette work requirements on control cigarette consumption, and vice-versa. These measures will indicate how greenwashing perceptions may increase smoking. Greater demand intensity for greenwashed cigarettes compared to nongreenwashed cigarettes would indicate that greenwashing would increase cigarette consumption even at the lower end of commercial price ranges. Greater demand elasticity for greenwashed cigarettes compared to nongreenwashed cigarettes would indicate that greenwashing would increase cigarette consumption at higher prices in the commercial market, even if greenwashing had little or no effect at lower prices. By examining reinforcer interactions (cross-price elasticity), demand analyses can inform the degree to which smokers would pay more for greenwashed cigarettes even if non-greenwashed cigarettes were available at a lower price.

- b. Secondary outcome variables.

Smoking Topography: We will collect six measures of smoking topography: total puff volume, mean puff volume, mean puff duration, mean inter-puff interval, mean maximum flow rate, and number of puffs. These data will be collected by ad lib smoking using our existing custom smoking topography system currently in use in our laboratory (IRB00107178). Our current research uses this topography system to help participants achieve a target volume per puff, but is already fully functional in its ability to measure topography of ad lib smoking. These measures will indicate the effect of greenwashing on how people smoke cigarettes in more damaging ways, for example, by smoking more deeply (greater puff volume), faster (greater maximum flow rate, lower inter-puff interval), or with increased time in lungs (greater puff duration).

- c. Statistical plan including sample size justification and interim data analysis.

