Analysis of Demand Curves: A paired-samples *t*-test will examine each demand metric, with data transformations of each demand metric if non-normally distributed (square root transform of Q0 and natural-log transform of α). We expect different demand profiles (greater demand intensity, and lower elasticity of demand) when cigarettes are greenwashed compared to control cigarettes.

Analysis of Cross-Price Elasticity: To calculate cross price elasticity of cigarettes, any instances of zero self administrations within a block will be coded as 0.5 because the logarithm

Date: February 18, 2023

Principal Investigator: [name].

Application Number: IRB00264306

NCT04595279

of zero is undefined. Then, a linear regression will be performed on the log10 of consumption means vs. the log10 of unit prices. The resulting slope of this regression line will be the cross-price elasticity.

Analysis of Smoking Topography: Paired-samples *t*-tests will be used to compare measures of smoking topography between the greenwashed and control cigarettes.

Statistical power:

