Using data from an ongoing operant demand study in our lab evaluating the substitutability of reduced-nicotine content cigarettes for full-nicotine cigarettes (grant R01DA042527), elasticity (α) of reduced-nicotine cigarettes was significantly greater than that of full-nicotine cigarettes (Cohen's $d = 1.33$). Although these analyses were limited to single-item demand (i.e. cigarettes not concurrently available), the same underlying principles are applicable to the current analysis. Assuming an effect size half as large ($d=.67$), a sample size of $N = 20$ would provide power $\geq 80\%$ (two-tailed; $\alpha=.05$) to detect a main effect of greenwashing tactics on demand metrics. Our proposed sample size of $N = 35$ would provide between 97-98% power in the current analyses comparing demand metrics between the cigarette packaging types, assuming an effect size of $d=0.67$ or 0.70 , respectively. A previous study comparing smoking topography of water pipe tobacco with and without graphic warning labels demonstrated significantly reduced total puff volume in the water pipe with the graphic warning label relative to the unlabeled pipe ($d=0.49$) (Maziak et al., 2019). Using the effect size from Maziak et al. (2019), which is comparable to the current approach, a sample size of $N = 35$ would provide $\geq 80\%$ power (two-tailed; $\alpha=.05$). Because the published topography data represent the smallest encountered effect size among the outcomes, we are powering the study to address this effect, which will provide a sample size that is beyond sufficiently-powered to address the aforementioned demand outcomes.

Demand metrics (demand intensity, demand elasticity, cross-price elasticity) and topography measures (total puff volume, mean puff volume, mean puff duration, mean inter-puff interval, mean maximum flow rate, and total puff number) will be compared between control and greenwashed cigarettes using paired-samples *t*-tests. Power analyses were performed for all primary behavioral economic and topography variables. Because topography measures showed the smallest anticipated effect based on published data ($d = 0.49$), we have conservatively based our sample size on topography. Despite this conservative estimation, if non-significant trends are observed suggesting potential effects, the proposed research will provide excellent data for informing power for future studies.

- d. Early stopping rules.

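### The between-brand comparison of cross-price elasticity is driven mainly by the shared equal-price session, so it should not carry the conclusion that smokers would pay more for greenwashed cigarettes

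*Combined protocol and SAP*

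**What the plan says.** Section 4a (Behavioral economics sessions) sets up seven sessions:

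- Equal price, 10 pulls each: "in one session, both types of cigarettes will be concurrently available for the same fixed, low behavioral price".
- Greenwashed dearer, three sessions: "the control cigarettes will be available for 10 pulls, while the greenwashed cigarettes will be concurrently available for 100, 1000, or 10000 pulls".
- Control dearer, three sessions: the mirror image, "in which price for control cigarettes is 100, 1000, or 10000 pulls across sessions", with greenwashed at 10 pulls. The equal-price session is not run again, because "the session in which both are available for 10 pulls will have already been conducted".

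Under either label the product is the same: "both brands of cigarettes (Brand A and Brand B) will be the same commercial brand of cigarette" (section 4a, Greenwashing Manipulations).

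Section 7c (Analysis of Cross-Price Elasticity) codes zeros as 0.5 and regresses log10 consumption on log10 price. "The resulting slope of this regression line will be the cross-price elasticity". The Statistical power part of 7c then puts this slope among the outcomes compared between brands by paired t-test: "Demand metrics (demand intensity, demand elasticity, cross-price elasticity) and topography measures".

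Section 7a, in a sentence that names cross-price elasticity as the means, says "demand analyses can inform the degree to which smokers would pay more for greenwashed cigarettes" when the other brand is cheaper. Section 3 (Background) makes the same statement. Neither 7a nor 7c gives a direction or a reading rule for the between-brand difference in slopes. Hypothesis (c) in section 2, more use of greenwashed cigarettes even at a higher price, has no named test in 7c.

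**The concern.** Cross-price elasticity describes what happens to the cheap brand as the other brand becomes dearer. It does not measure how much of the dearer brand is taken. Because one equal-price session starts both regressions, a preference shown only when prices are equal feeds directly into the difference between the two slopes. A significant paired test could then be reported as evidence that smokers would pay more for greenwashed packs when no participant did so. The study is meant to inform regulatory action, so a premium-price conclusion should rest on an outcome that can show a premium.

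**Working it through.** **The plan's own figures.** Exact paired t-test power (two-tailed, alpha .05) gives 80.4% for N = 35, d = 0.49; 97.1% and 98.0% for N = 35, d = 0.67 and 0.70; and 81.1% for N = 20, d = 0.67. All agree with section 7c and do not bear on this point.

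**Inputs.** From the documents: prices 10, 100, 1000 and 10000; one shared equal-price session; zeros coded 0.5; N = 35. Assumed, because the documents give no consumption data: 12 bouts in total per session, and one slope per participant and brand.

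**Step 1: slope weights.** The log10 prices are 1, 2, 3, 4 with mean 2.5. The deviations are -1.5, -0.5, 0.5, 1.5 and their squares sum to 5. The least-squares weights are therefore -0.3, -0.1, 0.1, 0.3. Let D be the greenwashed slope (on control price) minus the control slope (on greenwashed price). With G and C bouts at equal price, the shared session contributes -0.3 x log10(G/C) to D.

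**Step 2: everyone takes the cheaper brand whenever prices differ.** With T bouts per session, each brand's slope is -0.3 log10(own bouts at equal price) + (-0.1 + 0.1 + 0.3) log10 T = 0.3 x log10(T / own bouts at equal price). So D = -0.3 x log10(G/C), and T cancels. Nobody pays a premium here, yet:

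| Equal-price split (greenwashed:control) | D |
|---|---|
| 50:50 | 0.00 |
| 60:40 | -0.053 |
| 9:3 | 0.3 log10(12/9) - 0.3 log10(12/3) = 0.037 - 0.181 = -0.14 |
| 80:20 | -0.181 |
| 90:10 | -0.286 |

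**Step 3: noisy choice.** Let the log-odds of choosing greenwashed equal preference minus price slope x log10(greenwashed price / control price). Preference varies between persons with mean 0.5 and SD 1; there are 12 bouts per session and N = 35. The dearer-brand difference is greenwashed bouts when greenwashed is dearer minus control bouts when control is dearer, summed over three prices.

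| Price slope (logits per log10 price) | Mean D | Dearer-brand difference (bouts) |
|---|---|---|
| 1 | about -0.07 | about 4.2 |
| 5 | about -0.07 | about 0.12 |

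The paired test of D had 64-70% power across this range. Per session, the dearer-brand difference falls from 4.2/3 = 1.4 bouts to 0.12/3 = 0.04 bouts. D hardly changes while the quantity that expresses a premium almost vanishes. In a wider set of runs (10 to 40 bouts, two price sensitivities), the shared session made up about 83-98% of mean D for premiums of about 1.8 to 100 times the control price.

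**Step 4: monotonicity (secondary).** Take a smoker who chooses only greenwashed up to some price and only control above it, with 12 bouts and zeros coded 0.5. The greenwashed slope is 0, and log10(12/0.5) = 1.380.

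| Behaviour | D |
|---|---|
| Greenwashed at equal price only | -0.3 x 1.380 = -0.41 |
| Pays up to 100 pulls | -(0.3 + 0.1) x 1.380 = -0.55 |
| Pays up to 1000 pulls | -(0.3 + 0.1 - 0.1) x 1.380 = -0.41 |
| Always greenwashed | 0.00 |

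The same value arises for no premium and for paying 1000 pulls. In smooth choice models the reversal appeared only above roughly a 30-fold price ratio.

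**The case against.** The strongest reply is that the plan is more modest than the concern suggests. Section 7a defines cross-price elasticity as the effect of one brand's price on consumption of the other, which is substitution. It says only that the analysis can inform the premium question, and it never states that a significant slope difference shows a premium. The plan also estimates own-price demand for greenwashed cigarettes with control held at 10 pulls, and compares elasticity by paired t-test. Those sessions observe directly whether smokers work harder for greenwashed packs.

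Much of this stands. The design collects what is needed, and the criticism does not extend to the other demand metrics. It does not remove the point, for two reasons. Section 7c commits the slope to a between-brand test, and the only reading that 7a attaches to cross-price elasticity beyond its definition is the premium one. Own-price elasticity covers the question only in part: it describes how fast consumption falls with price, and no named test compares consumption at the higher prices.

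Two stronger readings are tempting and are not supported.

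- A reader might infer that the paired cross-price test is invalid and must be dropped. With no preference, it rejected in about 4-6% of simulated trials. A preference at equal price is a real greenwashing effect, not a false positive.
- A reader might infer that the strongest effect would give a null result. That needs every smoker to refuse control at 10 pulls while working 10000 pulls per bout for a physically identical cigarette. At an assumed 2 pulls per second, only 10800 / (5000 + 180) = 2.1 such bouts fit in three hours. It is a corner case.

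The simulated contrast also depends on price sensitivity. In a run with the same settings at price slopes of 1 and 2, the dearer-brand test had 78% and 69% power against 67-68% for the cross-price test, so the two broadly agreed. They part when the price response is strong, which identical cigarettes make plausible but the documents do not establish.

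**Conclusion.** The concern holds as a matter of interpretation. The between-brand difference in cross-price elasticity is a valid test of some greenwashing effect, but not a measure of willingness to pay more. The slope weights, the shared session and the full-switching result follow from the plan's own method. The size of the problem (a difference near -0.07 with 64-70% power while the dearer-brand difference falls from about 4.2 to 0.12 bouts) rests on the assumed 12 bouts, preference distribution and choice model. Non-monotonicity is real but secondary, because reversal needs very large premiums. Nothing here faults the session design, the own-price metrics or the power figures. The change is worth making because it alters what the trial can conclude about higher prices.

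**What to change.** 1. Add to section 7c a named paired test for the premium-price question: greenwashed bouts when greenwashed is the dearer brand minus control bouts when control is the dearer brand at the same price, averaged over 100, 1000 and 10000 pulls. This contrast leaves out the equal-price session and needs no zero coding. It asks whether smokers work more for greenwashed than for control under mirrored prices. If hypothesis (c) instead means more greenwashed than control bouts within the same session, the plan should say so and name that test.
2. Reword the sentence in section 7a, and its counterpart in section 3, so that cross-price elasticity is read as substitutability and any conclusion about paying more rests on the new contrast together with own-price demand.
3. The paired cross-price test may stay, with a statement that a difference is not to be read as willingness to pay more.

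The cost is plan wording and one additional test, with no new sessions or data. The test will have low power if dearer-brand consumption is near zero: about 19% at a price slope of 5 in the model above. A null result should then be reported with its confidence interval and not as evidence of no premium.

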Interested individuals will call the study contact number, and study personnel will conduct a brief screening for eligibility over the phone. To facilitate timely screening of participants for eligibility, website ads and flyers will contain a link to a brief online interest and eligibility survey using JHM Qualtrics. All individuals will be phone screened and, if qualified, scheduled for an in-person screening visit (approximately 2 hrs.) at the Behavioral Pharmacology Research Unit (BPRU) at the Johns Hopkins Bayview Medical Campus. Individuals will not sign consent before telephone screening. For those who meet phone screen eligibility, the laboratory screening will include physical and mental health history, drug history, physical examination, and standard laboratory tests of blood chemistry and hematology.

General Procedures: We will recruit and consent up to 100 individuals to accrue 35 non-treatment seeking male and female dependent cigarette smokers to complete the study by advertising and word-of-mouth. These volunteers will be medically healthy smokers without immediate intention to quit and will be fully informed community non-treatment seeking volunteers, who do not constitute a special vulnerable population. They will participate in a 9-session laboratory study at the Behavioral Pharmacology Research Unit at the Johns Hopkins Bayview Campus.

All lab visits will last approximately 4 hours total. Participants will be instructed to abstain from smoking for 6 hours before the beginning of each daily session in order to achieve a carbon monoxide (CO, a byproduct of smoking; measured by the Smokerlyzer, CoVita, Haddonfield, NJ, USA) measure $\leq 50\%$ of the CO value obtained at the initial screening. If a participant fails to meet this criterion, the session will be rescheduled (or participation discontinued after multiple such instances). Sessions will be conducted at various times throughout the day, but each

Date: February 18, 2023

Principal Investigator: [name].

Application Number: IRB00264306

NCT04595279

individual participant will always begin his or her sessions at the same time of day throughout the experiment.

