Topography sessions (Sessions 1-2): After assuring ≥ 6 hours of smoking abstinence via breath CO requirements, participants will take part in a 3-hour smoking topography session. In one session participants will have the ability smoke cigarettes associated with the greenwashing techniques, and in the other session participants will have the ability to smoke control cigarettes without the greenwashing technique used in labelling. Order of the two sessions will be randomized and counterbalanced across participants. Participants will be free to smoke cigarettes ad lib and in any manner they choose (e.g., depth and timing of inhalations) so long as they smoke the cigarettes through the small cigarette holder connected to our existing topography equipment (currently in use for IRB00107178). From this 3-hour session, topography measures to be determined include: total puff volume, mean puff volume, mean puff duration, mean inter-puff interval, mean maximum flow rate, and number of puffs.

At the conclusion of the second topography session, participants will practice the targeted puff volume smoking required of the following behavioral economic sessions. In contrast to the topography sessions, the behavioral economic sessions will require participants to achieve a target puff volume (70 ml) when they choose to self-administer cigarette puffs. This is because it is necessary to standardize puffs to ensure a constant reinforcer size across conditions. Product appeal will be assessed for both packages during these sessions.

Behavioral economics sessions (Sessions 3-9): In general, methods are modeled closely after those currently in place for research being conducted investigating reduced-nicotine

Date: February 18, 2023

Principal Investigator: [name].

Application Number: IRB00264306

NCT04595279

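### The topography t-tests ignore the counterbalanced session order; a pre-specified order term costs about 0.1 power point near balance and helps if order matters

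*Combined protocol and SAP*

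**What the plan says.** Section 4a, Topography sessions, schedules one ad-lib session with the greenwashed cigarettes and one with the control cigarettes: "Order of the two sessions will be randomized and counterbalanced across participants". Section 7c, Analysis of Smoking Topography, then says that paired-samples t-tests "will be used to compare measures of smoking topography between the greenwashed and control cigarettes". Section 7c, Statistical power, repeats this for all demand and topography measures, which "will be compared between control and greenwashed cigarettes using paired-samples" t-tests. No order, period or sequence term appears anywhere in Section 7c.

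Section 7b makes the six topography measures secondary. They nevertheless set the size of the study: "we have conservatively based our sample size on topography". The target is 35 completers, with d = 0.49, a two-tailed alpha of 0.05 and power of at least 80%.

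**The concern.** The design controls session order and the analysis then does not use it. Participants may smoke differently in session 2 than in session 1, for instance because they have become used to smoking through the measuring holder. If so, the greenwashed-minus-control differences are shifted up in one order group and down in the other.

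With nearly equal groups the shifts cancel in the mean but inflate the standard deviation that the paired t-test uses. With clearly unequal groups they no longer cancel. At stake are a few points of power in an analysis with 0.4 point of reserve above 80%, and the accuracy of the type I error.

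**Working it through.** **Inputs from the documents.** N = 35 completers (Section 4a, General Procedures). d = 0.49, two-tailed alpha 0.05 and power of at least 80% (Section 7c, Statistical power). The d comes from a water pipe study that "demonstrated significantly reduced total puff volume in the water pipe with the graphic warning label relative to the unlabeled pipe". I take it as standardised on an SD of within-participant differences; the plan does not define the scale.

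**Assumptions, because the documents give no figure.** The order effect e is the shift from session 1 to session 2 in SDs of the within-participant difference, tried at 0.2, 0.3 and 0.5. The last is about as large as the assumed treatment effect. The split by order among the 35 is 18/17 at best; 20/15 and 22/13 are illustrations.

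**Step 1: the plan's own figure.** For the paired t-test the noncentrality is d√N = 0.49 × √35 = 2.899, with 34 df and critical value 2.032. Power is 80.4%, so the plan's claim of at least 80% reproduces.

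**Step 2: cost of the order term if order has no effect.** Write m = (n1 - n2)/N. The order-adjusted estimate is the mean of the two order-specific mean differences. Its noncentrality is d√(N(1 - m²)), with 33 df.
- 18/17: m = 1/35, noncentrality 2.898, power 80.3% (cost 0.1 point).
- 20/15: m = 5/35, noncentrality 2.869, power 79.5% (cost 0.9 point).
- 22/13: m = 9/35, noncentrality 2.801, power 77.6% (cost 2.8 points).

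**Step 3: effect of a real order effect at 18/17.** The model is D = τ + e·s + error, with s = +1 or -1 by order. In units of the residual SD (the SD within an order group), the mean difference is normal with mean τ + e·m and variance 1/N. The sum of squares is noncentral chi-square with 34 df and noncentrality N·e²(1 - m²). Integrating the paired t-test over these gives the table. Ranges cover which order has the 18.

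| e | Paired t, type I error | Paired t power, d on residual SD | Order-adjusted | Gain (points) | Paired t power, d on total SD | Order-adjusted |
|---|---|---|---|---|---|---|
| 0.2 | 4.6% | 78.3-80.2% | 80.3% | 0.1-2.0 | 79.9-81.7% | 81.9% |
| 0.3 | 4.1% | 76.3-79.2% | 80.3% | 1.1-4.0 | 80.0-82.7% | 83.9% |
| 0.5 | 2.9% | 70.3-75.7% | 80.3% | 4.6-10.0 | 81.0-85.7% | 90.1% |

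The total SD includes the order variance, so the residual SD is then √(1 - e²). On the residual SD, averaged over the two possible 18/17 splits, the order term breaks even at e = 0.06. In the split that favours the paired t-test it breaks even at e = 0.18 and never loses more than 0.3 point.

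**Step 4: a clearly unequal split.** At 22/13 and e = 0.3 the unadjusted mean is shifted by 0.3 × 9/35 = 0.077 SD. Paired-t type I error is then about 6.2%, while the order-adjusted test holds 5%. Comparing the power of the two tests at such a split is not fair, because they no longer have the same size.

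**The case against.** The strongest case against is that nothing here is wrong. The test is valid over the randomisation, counterbalancing already protects the contrast, the stated power reproduces, and the outcomes are secondary. All of that stands, and it is why this is an improvement to consider and not a defect.

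The size of the gain is also unknown. The 5-to-10-point gain needs an order shift as large as the assumed treatment effect, and at 0.2 SD the gain is at most 2 points. The uncertainty in d is of similar size: at d = 0.48 the same formula gives 78.8%, a loss of 1.6 points. This limits what the change can achieve but does not make it a worse choice.

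A reader might infer more in two places:
- **That order puts the stated power at risk.** This requires d = 0.49 to exclude order variance. The plan does not say, and the reference list gives the source study's title as a crossover, so its d may well include it. In that case paired-t power stays at 79.9% or above in the table. Even on the residual SD, one of the two splits still gives 80.2% at e = 0.2.
- **That heavy attrition will unbalance the orders.** The plan will "recruit and consent up to 100 individuals to accrue 35 non-treatment seeking male and female dependent cigarette smokers to complete the study", but those consented may include people who fail screening and never receive an order. The figure says nothing about the split among completers.

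**Conclusion.** The point holds as a low-cost refinement. The analysis leaves out a factor that the design randomises. Putting it in costs 0.1 power point near balance if order is irrelevant. If order matters, it removes the conservatism at a near-equal split and the excess type I error at a clearly unequal one.

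The size of the benefit rests on assumed order effects and splits, and on how d = 0.49 was standardised, none of which the documents settle. The documents do not support calling the paired t-test invalid or the sample size wrong. The order term deals with a session-order shift only; with two sessions it cannot separate carry-over from the greenwashing effect.

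**What to change.** Before results are seen, state in Section 7c that each of the six topography measures will be tested by regressing the within-participant difference (greenwashed minus control) on session order coded +1/-1 and testing the intercept. Keep the paired t-test as a sensitivity analysis and leave the primary demand tests unchanged.

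The cost is a sentence or two of wording and one error degree of freedom. If order has no effect, the loss of power grows with imbalance, as in Step 2. Recruitment, randomisation and session procedures need no change. Fixing the model in advance also avoids a later choice between adjusted and unadjusted results across six outcomes.
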